4.3 Sub-analysis

- 1) To split the primary and secondary objectives by patients under 16 years of age and patients 16–65 years of age at the time of the index date.
- 2) To split the primary and secondary objectives by patients prescribed high dose (≥ 1000 μg of beclomethasone dipropionate and low dose < 1000 μg beclomethasone dipropionate).

5.0 Study design

5.1 Products studied

The medicinal product is non extra fine beclomethasone which provides 50, 100, 200 and 250 μg beclomethasone dipropionate per actuation in a pressurised MDI device.¹¹

The devices studied include the Volumatic[®] and Aerochamber[®] spacer devices.

5.2 Study design (questionnaire outcomes)

A longitudinal study to compare patient-reported side effects for asthma patients prescribed non extra fine beclomethasone with Volumatic[®] spacer or Aerochamber[®] spacer (Figure 4). The index date of the study is the date of administration of the BLF Questionnaire. This study design will also be used to explore patients who step down at the index date with Volumatic and Aerochamber spacers. This exploratory objective will explore the baseline year (ie: year before index) in terms of comparative efficacy. If required (due to insufficient patients) an additional study design will be incorporated which will consider date of step down as index date (instead of date of BLF questionnaire).

[figure not shown]

Figure 4: Study Design (questionnaire outcomes)

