4.0 Study aims and objectives

4.1 Study aims

The aim of this study is to characterise the adverse events in patients with asthma treated with non-extra fine beclomethasone dipropionate with Volumatic[®] spacer or Aerochamber[®] spacer.

In addition, as an additional question, the study will also attempt to explore whether

Aerochamber patients experience increased efficacy leading to their daily dose of non-EF beclomethasone being changed (stepped down or titrated down) compared to Volumatic users.

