5.4 Study design (database outcomes)

This is a historical database study composed of a 1-year baseline period for demographics, characterisation and matching. The index date is the date of prescription of a spacer (Volumatic[®] or Aerochamber[®]), with a 3-year outcome period for detection of adverse events. Patients will require 4 years' continuous practice data.

[figure not shown]

Figure 5: Study Design (database outcomes) extractions from 2005 onwards

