6.0 Study Population

6.1 Inclusion and exclusion criteria (questionnaire outcomes)

Inclusion criteria

Diagnosis for asthma (confirmed by diagnostic Read code)

Age ≤65 years at index date for main outcomes, all ages for exploratory

Two years of continuous practice data comprising 2-year data prior to questionnaire

Asthma questionnaire returned

Prescription of Aerochamber[®] or Volumatic[®] spacer prior to the questionnaire

≥2 separate prescriptions of non extrafine beclomethasone in the baseline year prior to the index date

Exclusion criteria

Received multiple types of ICS or FDC ICS/LABA during the baseline period or at the index date

Prescribed both Aerochamber and Volumatic spacers

Table 6: Inclusion and exclusion criteria for questionnaire outcomes

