7.1 Demographic and baseline variables for patient questionnaire outcomes

- Gender (male/female)

- Age of patient (years, at index date)
- Body Mass Index (BMI, at time nearest index date, calculated from height and weight data if available, otherwise taken from practice-recorded BMI value, detailed definition in Appendix 1)
- Smoking status (identified by Read code, closest to index date)
- SABA daily dose calculated 1 year prior to index date*
- Percentage predicted peak flow (closest to index date)
- Total cumulative ICS dose
- Spacer type
- Total cumulative non-extrafine beclomethasone dipropionate therapy
- Duration of ICS therapy
- Number of exacerbations (ATS/ERS 2015 consensus definition[†]) from 1 year prior to index date
- Number of oral corticosteroid prescriptions from 1 year prior to index date
- Number of antibiotic prescriptions for lower respiratory tract infections from 1 year prior to index date
- History of comorbidities related to asthma:
 - Pneumonia (Read code diagnosis from 1 year prior to the index date)
 - Diabetes (Read code diagnosis and/or antidiabetic drugs ever prior to the index date)
 - Ischaemic heart disease (Read code diagnosis before one year prior to the index date)
 - Rhinitis (Read code diagnosis, including chronic and allergic rhinitis and prescriptions for nasal steroids between one year prior to index date)
 - Eczema (Read code diagnosis between one year prior to index date)
 - Osteoporosis (Read code diagnosis between one year prior to the index date)
 - Charlson Comorbidity Index (based on Read code diagnoses between one year prior to index date, detailed definition in Appendix 1)

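### In the questionnaire cohort a spacer prescription of any age counts as exposure, while the matching covariates come from the year before the questionnaire and so can follow that exposure

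*Protocol*

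**What the plan says.** Protocol 5.2 fixes the time origin of the primary cohort: "The index date of the study is the date of administration of the BLF Questionnaire". The baseline year is the year before that date.

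Exposure is defined in 6.1 by one line: "Prescription of Aerochamber[®] or Volumatic[®] spacer prior to the questionnaire". The recency rule in the same table, "≥2 separate prescriptions of non extrafine beclomethasone in the baseline year prior to the index date", concerns the drug and not the spacer. The record requirement, "Two years of continuous practice data comprising 2-year data prior to questionnaire", is also tied to the questionnaire. Patients prescribed both brands are excluded.

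Section 7.1 lists the baseline variables, for example "SABA daily dose calculated 1 year prior to index date". Exacerbations, oral steroid prescriptions and antibiotics for lower respiratory infection use the same year. Section 8.3 draws the matching variables from these data, including markers of disease severity, and chooses them partly by how well they predict the primary outcome. It adds matching on high or low average ICS dose if numbers allow. Section 8.4.1 adjusts for baseline confounders.

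The database cohort is set up differently in 5.4: "The index date is the date of prescription of a spacer", with the baseline year before it.

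**The concern.** A confounder has to precede the exposure. Here the covariate window is placed relative to the questionnaire and the exposure can lie anywhere before it, so the window may sit after the patient began using the spacer. Matching on a variable that the spacer may have altered can remove part of the effect under study or introduce new bias.

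The Protocol itself treats some of these variables as possible spacer effects. Sections 5.2, 7.5 and 8.4.2 take exacerbations and SABA use in that same year, among patients who step down, and compare them between spacers as a measure of efficacy. Section 4.1 sets out to explore whether "Aerochamber patients experience increased efficacy leading to their daily dose of non-EF beclomethasone being changed".

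The second issue is the age of the exposure. The questionnaire asks about side effects the patient has now, but a spacer prescribed years ago counts the same as one in use. Section 3.0 acknowledges that patients may be unwilling to carry or use these devices. In a non-inferiority comparison, anything that makes the arms look alike can help the claim succeed.

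**Working it through.** **Timing.** The spacer must precede the questionnaire, so two cases cover the cohort:

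- Spacer first issued more than 12 months before the questionnaire: the whole covariate year follows exposure.
- Spacer first issued within those 12 months: the part of the year after the spacer date follows exposure.

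Nothing in 5.2, 6.1, 7.1 or 8.3 limits the spacer date or moves the covariates ahead of it. Sex, age and diabetes recorded at any earlier time are largely unaffected. The time-varying severity markers are affected.

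**The plan's own power figure.** Inputs from 8.1: groups of 293 and 147, proportion 0.30 in the standard group, expected difference 0, margin 0.13, one-sided 0.025.

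- SE = √[0.30 × 0.70 × (1/293 + 1/147)] = 0.0463
- Power = Φ(0.13/0.0463 − 1.96) = Φ(0.847) = 0.801

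The stated 80% is reproduced, so the same formula can be used for the next step.

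**Similar lapse in both arms.** Assumptions: a fraction f in each arm no longer uses the recorded spacer; lapsed patients have the same risk in both arms; the true excess among users is 0.13, read as an absolute difference as in 8.1; and the standard-arm proportion is held at 0.30. The observable difference is then d = 0.13 × (1 − f), and

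P(declare non-inferiority) = Φ((0.13 − d)/SE − 1.96), with SE = √[(0.30 + d)(0.70 − d)/n_T + 0.21/n_S].

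Example with f = 0.20, n_T = 293, n_S = 147: d = 0.104, SE = 0.0474, and Φ(0.026/0.0474 − 1.96) = Φ(−1.41) = 0.079.

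| Lapsed fraction f | Observable excess | 293 v 147 | 147 v 147 |
|---|---|---|---|
| 0% | 13.0 points | 2.5% | 2.5% |
| 10% | 11.7 points | 4.6% | 4.2% |
| 20% | 10.4 points | 7.9% | 6.8% |
| 30% | 9.1 points | 12.8% | 10.5% |
| 50% | 6.5 points | 28.1% | 21.9% |

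Section 8.1 does not say which arm has 293 patients; swapping the arms changes little (27.3% at f = 50%). The last column is included because 8.3 plans 1:1 matching.

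**Lapse in the Aerochamber arm only.** Let r0 be the risk without a spacer (an assumption). The difference becomes 0.13(1 − f) + f(r0 − 0.30). With f = 0.20:

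- r0 = 0.30: 0.104, the same false-positive risk as above
- r0 = 0.43: 0.104 + 0.026 = 0.130, risk 2.5%
- r0 = 0.50: 0.104 + 0.040 = 0.144, risk about 1.2-1.4%

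The table therefore depends on lapse being similar in the two arms.

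**The case against.** Several counter-arguments carry weight.

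- **Direction of stale exposure.** A reader might infer that old prescriptions necessarily favour non-inferiority. They do not. Patients prescribed both brands are excluded, so a lapsed Aerochamber patient has most likely gone to no spacer, and the Protocol gives no risk for that state. If lapse is confined to one arm, the bias can vanish or reverse.
- **Real-life use.** A spacer is a durable device, so an old prescription is not proof of non-use. The study compares prescribed combinations in practice, and some non-use may belong to the question. This stands, and is a reason to keep the any-time analysis.
- **Dose.** It is tempting to say that matching on ICS dose tilts the result towards non-inferiority. Section 4.1 only proposes to explore a dose change, and the change it names is a step-down with Aerochamber. If that lowered side effects, matching on dose would remove an Aerochamber benefit and work against the claim. Dose matching is also conditional on numbers.
- **Final matching list.** This may be settled in a SAP that is not shown. But the window is fixed in 7.1, and a selection rule based on predicting the outcome does not screen out variables that follow the spacer.
- **Database cohort as a template.** It is not a clean one. Section 5.4 indexes on a spacer prescription without requiring the first, and 6.2 also requires a step-down in the outcome period.
- **Figure 4.** It is not available and may show the windows, but the text of 5.2, 6.1 and 7.1 is explicit and sets no limit on the spacer date.

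**Conclusion.** The concern holds as a timing defect in the primary cohort. Exposure has no recency or co-use rule, and the time-varying covariates offered for matching and adjustment partly or wholly follow the spacer, although exacerbations and SABA use in that same year are also compared between spacers as outcomes. The direction of the bias from matching on them is unknown.

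The size of the stale-exposure effect is conditional. With similar lapse in both arms and a true 13-point excess, false non-inferiority is about 7-8% at 20% lapsed and 10-13% at 30%, against the nominal 2.5%. The lapsed fraction and its equality between arms are assumptions with no figure in the Protocol. The documents do not support a statement that the design is biased towards non-inferiority in general. They support saying that the primary conclusion rests on an untested assumption about when the spacer was issued and whether it is still used.

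**What to change.** Before matching, pre-specify a second, spacer-anchored analysis of the primary outcome, to run alongside the any-time analysis:

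- Include patients whose first recorded spacer prescription falls in the 12 months before the questionnaire and on or after their first beclomethasone prescription.
- Take matching and adjustment covariates from the 12 months before that spacer prescription. At most this reaches 12 + 12 = 24 months before the questionnaire, which the two years of records already required will cover.
- In this analysis, report average ICS dose in the year before the questionnaire descriptively, or use it only in a sensitivity adjustment.
- Describe non-inferiority as robust only if both analyses agree, and define agreement in advance.

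The cost is re-programming of windows in data already held. The spacer-anchored cohort will be smaller and its interval wider, and the loss cannot be quantified from the Protocol; this is why it is proposed beside the any-time analysis and not in its place. Two limits remain: two years of records cannot prove that the first recorded spacer was truly the first, and a recent prescription does not prove use.

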7.5 Step down outcomes

- 1) Number of severe exacerbations in baseline year
- 2) Daily average SABA category in baseline year

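### The exploratory step-down comparison reads the year before index as spacer efficacy, but the spacer need only precede the questionnaire, so most of that year can pre-date it

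*Protocol*

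**What the plan says.** Section 4.1 asks, as an additional question, whether better efficacy with Aerochamber leads to a reduction in beclomethasone dose, relative to Volumatic. Section 5.2 fixes the time axis: "The index date of the study is the date of administration of the BLF Questionnaire". It then fixes the window and the reading: "This exploratory objective will explore the baseline year (ie: year before index) in terms of comparative efficacy". If too few patients qualify, section 5.2 allows a second design with the step-down date as index.

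Section 7.5 lists the outcomes. The first is "Number of severe exacerbations in baseline year"; the second is the daily SABA category in the same year. Section 8.4.2 compares exacerbation rate and SABA dose between the two spacer groups with a Wilcoxon test.

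Eligibility for this cohort is in section 6.1:

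- Spacer: "Prescription of Aerochamber[®] or Volumatic[®] spacer prior to the questionnaire".
- Drug: "≥2 separate prescriptions of non extrafine beclomethasone in the baseline year prior to the index date".
- Records: "Two years of continuous practice data comprising 2-year data prior to questionnaire".
- Exclusion bearing on spacers: "Prescribed both Aerochamber and Volumatic spacers".

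**The concern.** An outcome can reflect a spacer's efficacy only if it occurs after the spacer is in use. Section 6.1 ties beclomethasone to the baseline year but does not tie the spacer to it. A patient first given an Aerochamber a month before the questionnaire is eligible, and a whole year of exacerbations and reliever use, most of it without the spacer, is then counted as the Aerochamber result.

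Two things follow. Any real difference between spacers is diluted by time when neither was in use. The contrast can also be biased, in either direction, if one group tends to have received its spacer more recently than the other, because the poor control being counted may be the reason the spacer was prescribed. A favourable result could then be taken as evidence of efficacy for a combination that Table 2 marks as fitting but not licensed.

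**Working it through.** **No protocol figure applies here.** The step-down question has no sample size. The only power statement (section 8.1: groups of 293 and 147, both proportions 0.300, margin 0.130, one-sided 0.025) concerns the primary outcome. It reproduces: the standard error is √[0.30 × 0.70 × (1/293 + 1/147)] = 0.0463, and 0.13/0.0463 − 1.96 ≈ 0.85 on the normal scale gives power of 80.1%. It plays no part in what follows.

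**Step 1: set the rules side by side.**

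| Element | Anchored to | Source |
|---|---|---|
| Outcomes | 12 months before index | 5.2, 7.5, 8.4.2 |
| Beclomethasone | at least two prescriptions within those 12 months | 6.1 |
| Spacer | any time before the questionnaire | 6.1 |
| Practice records | two years before the questionnaire | 6.1 |

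The spacer row is the only treatment element not tied to the outcome window. The records row governs availability of data, not exposure. Section 7.1 lists spacer type as a baseline variable but not spacer start date, and section 8.3 makes matching of step-down patients conditional on numbers. Nothing in the text restricts on, or adjusts for, time since first spacer.

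**Step 2: range of exposure under the main design.** Let d be the days from first spacer prescription to index. Exposed share = min(d, 365)/365; pre-spacer days = 365 − min(d, 365).

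| d (days) | Pre-spacer days | Share of year exposed |
|---|---|---|
| 1 | 364 | 0.3% |
| 30 | 335 | 8.2% |
| 90 | 275 | 24.7% |
| 182 | 183 | 49.9% |
| 365 or more | 0 | 100% |

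Every row satisfies section 6.1. The SABA dose in section 7.1 divides the year's supply by 365, so for d = 30 a share of 335/365 = 91.8% of that denominator is pre-spacer time.

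**Step 3: the fallback design.** Index moves to the step-down date and no spacer rule is restated. If the 6.1 criterion carries over as written, a spacer prescribed after step-down but before the questionnaire still qualifies. All 365 baseline days then precede it.

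**The case against.** The strongest reply is that this is an exploratory analysis. The title-page table and section 4.2.3 describe it only as comparing step-down patients on baseline exacerbations and SABA use, which is a description and not a causal claim. That limits the weight of the point, but does not remove it: sections 4.1 and 5.2 do speak of efficacy.

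Second, Figure 4, the diagram of this cohort, is not available to this review, and section 6.1 asks for two years of records where the baseline is one. The figure might mark spacer timing. No text does, however, and the written criterion is what selects patients.

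Third, a patient given a spacer for poor control a month ago is an unlikely candidate for step-down now, so the extreme rows of the table may be rare. That is fair, and the protocol offers no figure to settle it.

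Fourth, the protocol already expects that numbers may be insufficient, so a stricter rule could leave very few patients. This stands, and is why the fix offers an alternative.

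A reader might also want to put a size on the dilution. With an assumed true rate ratio of 0.80 and half the year exposed, simple mixing gives 0.5 × 1 + 0.5 × 0.80 = 0.90. The documents do not support that figure. It needs equal pre-spacer rates in the two groups, both equal to the on-Volumatic rate, and the same exposed share in each. The 0.80 is not in the protocol. Nor does a rate ratio describe a Wilcoxon test or a SABA category.

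**Conclusion.** The point holds: as written, the step-down analysis credits pre-spacer time to the spacer. The amount per patient can be anything from none to 364 of 365 days under the questionnaire index. It can reach the full year only under the fallback index, and only if the 6.1 criterion is left unchanged. The total effect on the comparison cannot be stated, because the distribution of spacer dates is not given. The direction of any bias is equally open.

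Three stronger inferences are not supported:

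- That the whole baseline year can precede the spacer under the main design. It cannot, since the spacer must come before the questionnaire.
- That the two-year rule in section 6.1 already places a spacer or beclomethasone prescription in the second prior year. It requires practice data only.
- That correcting the window would answer the question in section 4.1. The comparison would still be confined to patients who stepped down, so on its own it cannot show that Aerochamber leads to more step-down.

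The conclusion rests on the written text, without Figure 4. The primary non-inferiority analysis, the secondary analysis and the sample size are not affected.

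**What to change.** For the step-down analysis only, and under either index date:

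1. Make the efficacy comparison in patients whose first spacer prescription precedes the start of the 12-month baseline year. The exposed share is then 100% by this measure for everyone. The two years of records required by section 6.1 allow this to be checked. Under the fallback, count the record requirement back from the step-down date.
2. Report patients whose spacer began inside the baseline year separately.
3. If too few patients remain, count exacerbations and SABA supply only from the spacer date to index, with person-time as the denominator in place of the fixed 365 days.
4. Describe any comparison that includes pre-spacer time as baseline characterisation, not as spacer efficacy, and align the wording of sections 4.1 and 5.2 with that.
5. State in section 4.1 that a comparison among step-down patients alone cannot show whether either spacer leads to more step-down.

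Cost: one eligibility line and some rewording, using prescription dates held in the records. Item 1 leaves fewer step-down patients. Item 3 keeps them, but individual rates over short periods will be unstable.

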5.3 Sub analysis

1. Characterisation of patients in terms of demographics, baseline variables and patient-reported outcomes (BLF Questionnaire) by age group (<16, 16–65, all ages, >65 as an exploratory group)
2. Characterisation of patients in terms of demographics, baseline variables and adverse events by prescription for high daily ICS dose (>500 µg fluticasone equivalence/1000 µg beclomethasone dipropionate) defined as ≥1 prescription for 1000 µg beclomethasone dipropionate during the baseline period
3. Characterisation of patients in terms of demographics, baseline variables and patient-reported outcomes (BLF Questionnaire) by high daily ICS dose (>500

μg fluticasone equivalence/1000 μg beclomethasone dipropionate) calculated as an average daily ICS dose* during the baseline period

5.4 Study design (database outcomes)

This is a historical database study composed of a 1-year baseline period for demographics, characterisation and matching. The index date is the date of prescription of a spacer (Volumatic[®] or Aerochamber[®]), with a 3-year outcome period for detection of adverse events. Patients will require 4 years' continuous practice data.

[figure not shown]

Figure 5: Study Design (database outcomes) extractions from 2005 onwards

5.5 Sub analysis

1. Characterisation of patients in terms of demographics, baseline variables and adverse events by age group (<16, 16–65, all ages, >65 as an exploratory group)
2. Characterisation of patients in terms of demographics, baseline variables and adverse events by prescription for high daily ICS dose (>500 μg fluticasone equivalence/1000 μg beclomethasone dipropionate) defined as ≥ 1 prescription for 1000 μg beclomethasone dipropionate during the baseline period
3. Characterisation of patients in terms of demographics, baseline variables and adverse events by high daily ICS dose (>500 μg fluticasone equivalence/1000 μg beclomethasone dipropionate) calculated as an average daily ICS dose[†] during the baseline period

* Average daily ICS dose will be calculated as: $\sum(((\text{Count of inhalers} * \text{doses in pack}) / \text{baseline period}) * \text{mcg strength})$

† Average daily ICS dose will be calculated as: $\sum(((\text{Count of inhalers} * \text{doses in pack}) / \text{baseline period}) * \text{mcg strength})$

